Based on a limited number of reports in the clinical development programme for liraglutide 3.0 mg, a numerical imbalance was observed for events of breast neoplasms in females and colorectal adenomas in males. There were too few cases to determine whether these cases were related to liraglutide. In addition, there are insufficient data to determine whether liraglutide has an effect on pre-existing breast neoplasia. Two positively adjudicated cases of malignant colorectal carcinoma were reported in liraglutide-treated subjects and none in placebo-treated subjects.

Heart rate increase

In the clinical development programme, mean increase in resting heart rate (by 2-3 beats per minute) as well as a slight decrease in systolic blood pressure has been observed. The long-term clinical effects of the increase in resting heart rate have not been established. There is no indication that the effect on resting heart rate is dose dependent and the increase in heart rate disappears upon treatment discontinuation. When initiating treatment with liraglutide 3.0 mg, heart rate should be monitored at regular intervals consistent with usual clinical practice.

Allergic reactions

As in the case with all protein-based pharmaceuticals, treatment with liraglutide may evoke allergic reactions. These may include urticaria, rash, pruritus as well as anaphylactic reactions. As a precaution, subjects with known or suspected hypersensitivity to trial product(s) or related products will not be enrolled in the trial. In addition, subjects will be instructed to contact the site staff as soon as possible for further guidance if suspicion of a hypersensitivity reaction occurs

Pancreatitis

An association between the use of GLP-1RAs and pancreatitis has been suggested based on case reports received in clinical trials and during the post-marketing experience with liraglutide (in T2DM) and other GLP-1RAs. Few events of pancreatitis have been reported in clinical trials with liraglutide in weight management. After initiation of liraglutide 3.0 mg, subjects must be observed carefully for signs and symptoms of pancreatitis (see Section [8.8.1](#)). If pancreatitis is suspected, liraglutide 3.0 mg should promptly be discontinued and appropriate management should be initiated. If pancreatitis is confirmed, liraglutide 3.0 mg should not be restarted. Subjects with a history of pancreatitis are excluded from participation in the trial.

Acute gallstone disease

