#### **Definition of estimands**

#### Effectiveness estimand

The primary estimand is an effectiveness estimand (*de facto*) quantifying the average treatment effect of liraglutide 3.0 mg relative to placebo 56 weeks after randomisation, as adjunct to reduced caloric diet, increased physical activity and CMS-IBT, in all randomised subjects regardless of adherence to treatment.

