#### Efficacy estimand

A secondary efficacy estimand (*de jure*) is quantifying the average treatment effect of liraglutide 3.0 mg relative to placebo 56 weeks after randomisation, as adjunct to reduced caloric diet, increased physical activity and CMS-IBT, if all randomised subjects had adhered to assigned treatment regimen for the entire duration of the trial.

#### Effectiveness estimand at week 16

In addition, an effectiveness estimand (*de facto*) is quantifying the average treatment effect of liraglutide 3.0 mg relative to placebo 16 weeks after randomisation, as adjunct to reduced caloric diet, increased physical activity and CMS-IBT, in all randomised subjects regardless of adherence to treatment.

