#### Primary approach for handling of missing values

The primary approach for multiple imputations of missing values of body weight at week 56 (type MT+MD) for both the liraglutide 3.0 mg and placebo group is by sampling among all available assessments at week 56 in the placebo group (type AT+AD). This approach is also known as jump to reference and makes the assumption that subjects instantly after discontinuation lose any effect of randomised treatment beyond what can be expected from placebo treatment as adjunct to diet and exercise. Body weight measurements at visits between baseline and week 56 are not used for this imputation approach. The multiple imputation approach is done in three steps.

- **Imputation**: Step 1 defines an imputation model based on placebo subjects, which is used to impute missing body weight values at week 56 in both arms. This will be done 100 times and results in 100 complete data sets. A more detailed explanation of this step is given below.
- Analysis: Step 2 analyses each of the 100 complete data sets, using the statistical model defined in Section 2.3.1.1 and 2.3.1.2 and saves the 100 estimation results.

• **Pooling**: Step 3 integrates the 100 estimation results into a final result using Rubin's formula. The imputation model in step 1, uses placebo subjects from FAS with non-missing body weight measurements at baseline and week 56. The imputation model is a linear regression of body weight

Statistical Analysis Plan Trial ID: NN8022-4274 UTN: U1111-1177-5059 EudraCT No.: 2015-005592-24	CONFIDENTIAL	Date: Version: Status: Page:	07 July 2018 1.0 Final 13 of 24	Novo Nordisk
---	--------------	---------------------------------------	--	--------------

(kg) at week 56 on the factors and covariates listed in Table 2–4 (except randomised treatment) with no interactions. The estimated posterior distribution for the parameters (regression coefficients and variances) in the imputation model is then used to impute missing week 56 body weight values for both randomised treatment arms.

If 100 copies are not sufficient to establish stable results, a higher number will be used. The multiple imputations will be generated using Novo Nordisk trial number 80224274 as seed number.

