#### 2.4 Secondary endpoints

#### 2.4.1 Confirmatory secondary endpoints

Confirmatory secondary endpoints are listed in Section 4.2.2.1 in the protocol.

All confirmatory secondary endpoints, except proportion of subjects losing at least 4% of baseline body weight at week 16, are planned to be assessed at week 56 and will be analysed using the same primary MI approach as used for the primary endpoints and to address the effectiveness estimand. The statistical model for continuous confirmatory secondary endpoints will be ANCOVA with covariates listed in Table 2–4 with baseline body weight replaced by baseline measurement of endpoint to be analysed. Binary confirmatory secondary endpoints will be analysed using logistic regression in the same way as for 5% responders.

The effectiveness estimand at week 16 will be assessed using the confirmatory secondary endpoint of proportion of subjects losing at least 4% of baseline body weight at week 16. Subjects with missing values for weight at week 16 will be considered non-responders.

Sensitivity analyses will be carried out for all confirmatory secondary endpoints, except for proportion of subjects losing at least 4% of baseline body weight at week 16. See Table 2–6 for details on planned analysis methods, multiple imputation approach and sensitivity analyses.

The efficacy estimand will also be assessed for confirmatory secondary endpoints, except for proportion of subjects losing at least 4% of baseline body weight at week 16, using MMRM as described for the primary endpoints.

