#### 2.4.3.2 Safety endpoints

Descriptive statistics for all safety endpoints will be provided with the aim to compare liraglutide 3.0 mg and placebo. All analyses and tabulations will be done using the safety analysis set. Unless otherwise stated, no formal statistical analyses are planned for the safety endpoints.

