#### Pulse

Pulse (beats/min) at baseline and change of pulse at week 56, will be summarised in tables by week and treatment. Additionally, categories based on the maximum change from baseline until week 56 (>0, >5, >10, >20 beats/min) and categories based on the maximum value until week 56 (>80, >90, >100 beats/min) will be included in summary tables. Additionally, change in pulse from baseline to week 56 will be evaluated in the trial observation period similar to the primary analysis for the primary estimand but using the safety analysis set.

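### The only modelled pulse result mixes on-drug, off-drug and placebo-imputed subjects, so it understates the on-drug heart-rate rise, and no on-drug estimate is planned beside it

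*SAP*

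**What the plan says.** For safety in general, SAP 2.4.3.2 is descriptive: "Unless otherwise stated, no formal statistical analyses are planned for the safety endpoints". Pulse is one of the stated exceptions. Its modelled analysis reads "change in pulse from baseline to week 56 will be evaluated in the trial observation period similar to the primary analysis" for the primary estimand, using the safety analysis set; Protocol 17.4.3.2 has the same text. The primary estimand is the effectiveness estimand, defined "in all randomised subjects regardless of adherence to treatment". In the primary approach (SAP 2.3.2.2), imputation of missing week-56 values, for drop-outs and for subjects still on drug alike and in both arms, "is by sampling among all available assessments at week 56 in the placebo group (type AT+AD" categories).

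The other pulse outputs are tables by week and treatment, categories of maximum change (>0, >5, >10, >20 beats/min) and categories of maximum value (>80, >90, >100 beats/min). None is limited to time on drug.

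On-treatment views exist elsewhere in the SAP:

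- The MMRM in SAP 2.3.3 targets the effect "if all randomised subjects had adhered to assigned treatment regimen for the entire duration of the trial". It covers the primary endpoints and, under SAP 2.4.1, "The efficacy estimand will also be assessed for confirmatory secondary endpoints" apart from the week-16 responder endpoint. Pulse is in neither group.
- The on-drug period in SAP 2.4.3.2 is defined for adverse events only.

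Protocol 18.1 lists heart-rate increase among the risks, describes a "mean increase in resting heart rate (by 2-3 beats per minute"), says its long-term clinical effects are not established, and states that "the increase in heart rate disappears upon treatment discontinuation".

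**The concern.** Treating drop-outs like placebo is cautious for weight loss, because it shrinks a benefit; the sample-size section of the SAP describes the corresponding assumption as conservative. For a harm the same rule works the other way. On the sponsor's own statement that the rise disappears off drug, each liraglutide subject who has stopped by week 56 contributes no drug effect. Each missing liraglutide value is replaced by a placebo-like one, even when the subject was still injecting.

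The treatment-policy result answers a real question: what happens to pulse on average after assignment to liraglutide, whether or not it is continued. It does not answer how much pulse rises while a person takes the drug. A prescriber will ask that about a named risk with uncertain long-term consequences. As written, the only pulse difference with a confidence interval is reduced by stopping and missingness, and no modelled figure without that reduction is planned.

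**Working it through.** **The plan's own dilution, for weight (SAP 2.1).** Inputs: completer means −9 and −4, SD 7, 30% discontinuing, drop-outs behaving like placebo, 141 per arm.

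- Liraglutide mean: 0.7 × (−9) + 0.3 × (−4) = −7.5
- Difference: −7.5 − (−4) = −3.5, which is 0.7 × (−5)
- Liraglutide SD: √(49 + 0.7 × 0.3 × 25) = 7.37, stated as 7.4
- Standard error: √((7.4² + 7.0²)/141) = 0.858; power ≈ Φ(3.5/0.858 − 1.96) = 98.3%

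The stated −3.5 and 98.3% reproduce. The plan therefore already accepts that 30% discontinuation with placebo-like outcomes removes 30% of a difference. It states no corresponding figure for pulse.

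**The same arithmetic for pulse.** Let δ be the on-drug difference from placebo at week 56. Split the liraglutide arm into three parts:

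| Group at week 56 | Share | Expected difference from placebo |
|---|---|---|
| On drug, measured (AT) | 1 − d − m | δ |
| Off drug, measured or missing (AD, MD) | d | 0 (effect gone, or drawn from placebo) |
| On drug, missing (MT) | m | 0 (drawn from placebo) |

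Modelled difference = (1 − d − m) × δ, so the ratio to the on-drug difference is 1 − (d + m).

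**Values for d and m.** The documents cannot give the shares for this trial, so these are illustrations:

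- d = 25%: liraglutide discontinuation in trial NN8022-1839 (SAP 2.1). This is another trial, and it counts discontinuations rather than subjects off drug at week 56.
- d = 30%: the planning ceiling in SAP 2.1.
- d = 20%: an assumption that allows for restarters, whom SAP Table 2–1 counts as on treatment.
- m = 5% of the arm: an assumption.

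| d | Subjects of 141 | Ratio, m = 0 | Ratio, m = 0.05 |
|---|---|---|---|
| 0.20 | 28 | 0.80 | 0.75 |
| 0.25 | 35 | 0.75 | 0.70 |
| 0.30 | 42 | 0.70 | 0.65 |

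**Check by simulation.** With 141 per arm, 1,500 runs, the imputation model fitted in placebo, ANCOVA on baseline and δ set to 1, the mean estimates were 0.80, 0.75 and 0.70 for d = 0.20, 0.25 and 0.30 with m = 0. They were 0.75 and 0.65 for d = 0.20 and 0.30 with m = 0.05 (Monte Carlo error 0.003). At d = 0.25 the result was 0.75 whether every off-drug subject returned or none did. The zero off-drug effect and placebo imputation are inputs, so this confirms that the planned procedure behaves as the algebra says. It is not separate evidence on the size of d or m.

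**Why no loss in beats/min is given.** Protocol 18.1 does not say whether its 2–3 beats/min is measured on drug or is placebo-adjusted, so it cannot safely be used as δ.

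**The case against.** The strongest reply is that nothing here is an error. The in-trial comparison is a valid treatment-policy estimate and keeps the protection of randomisation. Safety is descriptive by default, so a modelled pulse analysis already goes further than usual, and amylase and lipase get the same in-trial treatment. That is right, and the in-trial analysis should not be replaced.

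Second, other outputs help. Early by-week tables come when fewer subjects have stopped, and a later off-drug reading cannot lower a peak reached on drug, so the maximum-change and maximum-value categories are less affected. This narrows the gap, but none of these outputs gives an on-drug mean difference with an interval.

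Third, the percentages are not trial data, and practical importance is not shown. With an assumed pulse SD of 9, the unadjusted 95% half-width is 1.96 × 9 × √(2/141) = 2.1 beats/min (1.6 to 2.6 for SD 7 to 11). If 2–3 beats/min were the on-drug difference, a loss of 20% to 35% would be about 0.4 to 1.05 beats/min, inside that half-width. This is fair and is a reason to rate the point low. The reduction is nevertheless systematic and in a known direction.

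Fourth, reading the pulse analysis as including placebo imputation is an inference from its being modelled on the primary analysis. It is the natural reading. Without it, off-drug readings from subjects who return would still dilute the estimate; the part due to placebo imputation depends on the reading.

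Last, an on-drug analysis has its own weaknesses: subjects may stop because of intolerance, and the MMRM estimates a hypothetical effect. That is why it should be supportive only.

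**Conclusion.** The concern holds. The single modelled pulse estimate is drawn towards no difference by the fraction of the liraglutide arm that is off drug or missing at week 56, and the plan has no on-drug counterpart with a confidence interval.

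The relative loss equals that fraction: about 20% to 30% in the illustrations, or 25% to 35% if another 5% of the arm is missing while on drug. This rests on three assumptions: no effect remains off drug, as Protocol 18.1 says; those who stop would have had a similar on-drug effect to those who continue; and the pulse analysis uses the primary placebo-based imputation. The actual fraction is unknown, so these are not forecasts for this trial.

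Pulse is a supportive safety endpoint and no confirmatory conclusion changes. This is an optional improvement.

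**What to change.** Keep the in-trial analysis and label its result as including off-drug and placebo-imputed subjects. Add to the Pulse part of SAP 2.4.3.2:

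> As a supportive analysis, change in pulse at the scheduled pulse visits will be analysed in the safety analysis set with an MMRM as in Section 2.3.3, with baseline pulse in place of baseline body weight, using values up to first discontinuation of trial drug (a pause of eight or more consecutive days). This analysis targets the effect had all subjects adhered, under a missing-at-random assumption. By-week summaries will be repeated using all on-drug values, including those after restart (exposure intervals, without the 14-day adverse-event window).

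Present the in-trial and on-drug results side by side.

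The cost is a paragraph of SAP text, one model and one repeated table. The model form is already specified, and Protocol 8.7 already has sites record stop and restart dates for pauses longer than one week, so no new data are needed. The number of pulse visits is in the flow chart, which was not in the text reviewed; the planned by-week tables suggest more than one. The MMRM drops values after a restart, and for that reason the repeated table includes them. Neither addition is fully protected by randomisation, so both should be described as supportive.

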#### ECG

Shifts in the ECG category from screening to week 56 will be summarised in tables.

#### Laboratory measurements

Laboratory values below the lower limit of quantification (LLOQ) will be set to ½LLOQ.

Laboratory safety parameters are measured throughout the trial and comprise haematology and biochemistry as defined in the flow chart.

The distribution of each continuous laboratory parameter will be presented using box plots by treatment and week. Continuous laboratory parameters will be compared to the relevant reference ranges and results will be presented.

Statistical Analysis Plan		Date:	07 July 2018	Novo Nordisk
Trial ID: NN8022-4274	CONFIDENTIAL	Version:	1.0	
UTN: U1111-1177-5059	CONFIDENHAL	Status:	Final	
EudraCT No.: 2015-005592-24		Page:	22 of 24	

#### Amylase and lipase

Shifts from baseline to highest value in trial period to UNL, 2xUNL and 3xUNL will be summarised in tables.

Mean plots, geometric mean plots and box plots by gender, visit and treatment will be prepared. Change from week 0 to week 56 will also be presented by empirical distribution plots.

Number and percentage of subjects with amylase and lipase levels  $\geq$ UNL,  $\geq$ 2xUNL or  $\geq$ 3xUNL will be tabulated by week and treatment. Subjects with values  $\geq$ 2xUNL will additionally be presented with spaghetti plots.

Additionally, change in amylase and lipase from baseline to week 56 will be evaluated in the in trial observation period similar to the primary analysis for the primary estimand but using the safety analysis set.

#### Calcitonin

Number, percentage and incidence of subjects with persistent (all post-baseline measurements) and incidental (at least one post-baseline measurement) increases in calcitonin for the criteria below will be tabulated for all subjects, males and females.

- From baseline  $\leq$ UNL to  $\geq$ UNL
- From baseline  $\leq$ UNL to  $\geq$ 20 ng/L
- From baseline <UNL to  $\ge$ 50 ng/L
- From baseline <20 ng/L to  $\ge 20 \text{ ng/L}$
- From baseline <50 ng/L to  $\ge 50 \text{ ng/L}$

Number and percentage of subjects with calcitonin levels  $\geq$ UNL,  $\geq$ 1.5xUNL or  $\geq$ 20 ng/L and  $\geq$ 50 ng/L will be tabulated by visit and treatment.

A summary table showing number and percentage of observations < and  $\ge$  LLOQ, minimum, Q25, median, Q75, maximum and geometric mean will be prepared by gender, visit and treatment.

The distribution of the calcitonin values across treatment group and time will be shown in plots by gender and total actual levels. Geometric means will be plotted by visit and treatment in order to assess the pattern of the longitudinal changes.

In addition, a scatter plot of baseline vs. maximum post-baseline calcitonin value will be prepared.

Longitudinal changes with calcitonin  $\geq 20$  mg/L will be evaluated with spaghetti plots.

Subjects with at least one post-baseline calcitonin value above 20 ng/L will be listed.

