Appendix A

NN8022-4274

Monitoring of calcitonin

~~This confidential document is the property of Novo Nordisk. No unpublished information contained herein may be disclosed without prior written approval from Novo Nordisk. Access to this document must be restricted to relevant parties.~~

Table of Contents

| | Page |
|--|-------------|
| Table of Contents | 2 |
| 1 Calcitonin monitoring | 4 |
| 1.1 Calcitonin \geq 100 ng/L..... | 4 |
| 1.2 Calcitonin \geq 50 and $<$ 100 ng/L..... | 4 |
| 1.3 Calcitonin \geq 10 and $<$ 50 ng/L..... | 5 |
| 2 References | 6 |

Background

Treatment with GLP-1 receptor agonists has shown to be associated with thyroid C-cell changes in rodents but not in non-human primates. The human relevance of this finding is unknown. However, based on the findings in rodents, monitoring of serum calcitonin (a sensitive biomarker for C-cell activation) is currently being performed in clinical trials with liraglutide.

While there is general agreement on the clinical interpretation of substantially elevated calcitonin levels (greater than 100 ng/L) is likely indicative of C-cell neoplasia; the interpretation of values between upper normal range (5.0 and 8.4 ng/L for women and men, respectively) and 100 ng/L is less clear with regards to indication of the neoplasia.

There are several known confounding factors affecting calcitonin levels, e.g.:

- renal dysfunction
- smoking
- autoimmune thyroiditis
- several drug classes (e.g. proton pump inhibitors, beta-blockers, H₂-blockers and glucocorticoids)

Physiology of C-cell activation in various clinical conditions and in different patient populations (i.e. with various co-morbidities) is poorly understood. There may be various clinical conditions not identified so far which mildly or moderately affect calcitonin secretion by C-cells.

1 Calcitonin monitoring

A blood sample will be drawn at pre-specified trial visits for measurement of calcitonin.

In case a subject has a calcitonin value ≥ 10 ng/L, the algorithm outlined below should be followed. The algorithm applies for all calcitonin values including screening values.

Please report clinically significant abnormal values as an adverse event (see Section 12 in the protocol).

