#### 2.1 Sample size calculation

The sample size calculation is based on the analysis approach addressing the primary estimand for the primary endpoints change in body weight (%) from baseline to week 56 (% weight change) and proportion of subjects losing  $\geq$  5% of baseline body weight at week 56 (5% responders).

The two primary endpoints will be tested in a hierarchical order.

The study design is a 1:1 randomisation with 282 subjects in total (141 subjects in each arm). Please see Table 2–2 for general specifications on sample size and power calculation.

 Table 2–2
 General specifications for sample size and power calculation

Endpoint	Statistical test	Minimum required power (%)
% weight change	Two-group Satterthwaite unpooled t test	90.0 (marginal)
	on the mean difference with $\alpha = 0.05$	
	assuming unequal variances	
5% responders	Pearson chi-square test for two	90.0 (marginal)
	independent proportions with $\alpha$ =0.05	

 $\boldsymbol{\alpha} {:} \text{ two-sided significance level}$ 

In the following paragraphs treatment differences and standard deviations (SD) are given without units.

Statistical Analysis Plan		Date:	07 July 2018	Novo Nordisk
Trial ID: NN8022-4274	CONFIDENTIAL	Version:	1.0	
UTN: U1111-1177-5059	CONFIDENTIAL	Status:	Final	
EudraCT No.: 2015-005592-24		Page:	9 of 24	

Body weight measurements from returning discontinuing subjects will be used in the primary analysis. But for the sample size calculations, it is assumed that all subjects who discontinue will not return at week 56 and that they have a % weight change like placebo subjects who completed the trial. It is expected that % weight change for liraglutide 3.0 mg subjects who discontinue might be somewhere in between completing placebo subjects and completing liraglutide 3.0 mg subjects. The assumption is thus expected to lead to a conservative effect estimate. In trial NN8022-1839 in non-diabetic subjects and with obesity, around 31% treatment discontinuations were observed in the placebo group, around 25% in the liraglutide 3.0 mg group. The calculated sample size ensures adequate power if the proportion of discontinuing subjects should be as high as 30%.

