#### 2.2 Definition of analysis sets

Two analysis sets are defined:

- The *full analysis set* (FAS) includes all randomised subjects according to the intention-to-treat (ITT) principle. Subjects in the FAS will be analysed as randomised.
- The *safety analysis set* includes all randomised subjects exposed to at least one dose of trial drug. Subjects will be analysed as treated.

Any observation excluded from the analysis database will be documented before database lock with the reason for exclusion provided.

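### The persistent-rise row for calcitonin excludes any lasting rise that starts after the first post-baseline sample, yet accepts a subject whose only post-baseline value is raised

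*SAP*

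**What the plan says.** The Calcitonin paragraph of SAP 2.4.3.2 plans a table of: "Number, percentage and incidence of subjects with persistent (all post-baseline measurements) and incidental (at least one post-baseline measurement) increases in calcitonin". Protocol 17.4.3.2 has the same definition, so the SAP did not introduce it. The table applies five shift criteria, for all subjects and by sex: from baseline below the upper normal limit (UNL) to the UNL, to 20 or to 50 ng/L; from below 20 to at least 20 ng/L; and from below 50 to at least 50 ng/L.

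Neither document adds a minimum number of values, a consecutive-value rule, a rule running from first rise to last value, or a statement on samples taken after trial product is stopped. The safety analysis set (SAP 2.2) "includes all randomised subjects exposed to at least one dose of trial drug", so subjects with a short series are included. On timing, Appendix A says: "A blood sample will be drawn at pre-specified trial visits for measurement of calcitonin". The visits are in the protocol flow chart, which is not in the text available for this review. Appendix A gives the upper normal range as "5.0 and 8.4 ng/L for women and men, respectively".

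The other planned calcitonin displays are:
- counts by visit and treatment at the UNL, 1.5 times the UNL, 20 and 50 ng/L
- summary statistics, distribution plots and geometric means over time
- a scatter plot of baseline against the post-baseline maximum
- spaghetti plots for values from 20 ng/L (the SAP prints mg/L; the protocol has ng/L)
- a listing of subjects with any post-baseline value above 20 ng/L.

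**The concern.** A reader of the safety table will take *persistent* to mean that the rise lasted. The rule instead asks whether the rise was already present at the first post-baseline sample and was never absent afterwards. An effect that builds over time would produce normal values early and raised values later, and the rule bars exactly that pattern. At the other extreme, one raised value with nothing after it says nothing about duration, yet it earns the label.

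Appendix A explains the interest in the marker: "monitoring of serum calcitonin (a sensitive biomarker for C-cell activation) is currently being performed in clinical trials with liraglutide". It also says that values between the upper normal range and 100 ng/L are harder to interpret than values above 100 ng/L. In that range it helps to know whether a rise stayed, and this is the only planned table that claims to separate lasting from passing rises.

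**Working it through.** The documents give no power, sample size or expected count for this table, so there is no figure to reproduce. The check applies the rule literally.

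**Inputs.** The two definitions come from SAP 2.4.3.2. The number of planned post-baseline samples, K, is an assumption because the flow chart is not available. Repeated sampling is nevertheless clear: the SAP says safety laboratory parameters are measured throughout the trial and tabulates calcitonin by visit, and Appendix A 1.3 refers to continued sampling.

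**Step 1: classify series (1 = criterion met, 0 = not met), with K = 4 as illustration.** The last column is the row proposed under the fix.

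| Post-baseline series | Every value raised (present persistent row) | At least one raised (incidental row) | Proposed row |
|---|---|---|---|
| 1,1,1,1 | yes | yes | yes |
| 0,1,1,1 | no | yes | yes |
| 0,0,1,1 | no | yes | yes |
| 0,0,0,1 | no | yes | no (unconfirmed) |
| 0,1,0,0 | no | yes | no |
| 1,1,1,0 | no | yes | no |
| 1 only | yes | yes | no (reported separately) |

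At present 0,1,1,1 and 0,1,0,0 receive the same label, although one rise lasts and the other passes. The single-value series receives the same label as 1,1,1,1.

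**Step 2: general K.** A late rise that continues starts at sample j, with j from 2 to K, which gives K − 1 patterns. Each contains at least one early 0, so none meets the present rule. For K = 2, 3, 4, 5 and 6 that is 0 of 1, 2, 3, 4 and 5 patterns. With K = 1 the two present categories coincide.

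**Step 3: what the proposed rule recovers.** A rise starting at sample j has K − j + 1 raised values. At least two are needed, so j can be at most K − 1, and K − 2 of the K − 1 patterns qualify: 0 of 1 for K = 2, 1 of 2 for K = 3, 2 of 3 for K = 4. With only two samples the old and new rules agree on 0,1, on 1,0 and on 1,1. Only the handling of single-value subjects would then change.

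**Step 4: effect of series length.** Under the present rule, once a subject has one value, each further sample can remove the persistent label but never grant it. This needs no assumption about rates or about independence between visits.

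**Step 5: off-drug samples.** Protocol 5.4 and 8.1 ask subjects who stop trial product to keep attending visits. A rise present throughout treatment that resolves after stopping is the series 1,1,1,0, which loses the label if the last sample counts. The documents do not say whether it does.

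**Step 6: what the other displays cover.** From about 20 ng/L, the spaghetti plots and the listing show each subject's course. Between the UNL (5.0 ng/L in women, 8.4 ng/L in men) and 20 ng/L, the plan has counts and summaries by visit, group plots and the scatter against the maximum. None of these links a subject's values over time.

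**The case against.** The definition is explicit, prespecified and the same in both documents. The table is descriptive, and SAP 2.4.3.2 plans no formal test for it. The categories are nested, so a late lasting rise is still counted in the at-least-one row. A subject at 20 ng/L or more at every later visit would appear individually in the spaghetti plots and, above 20 ng/L, in the listing. Geometric means by visit are planned to show the longitudinal pattern. The actions in Appendix A depend on individual values, not on this label. All of this stands and keeps the point small. It does not close the gap between the UNL and 20 ng/L.

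A reader might go further and infer that drop-out differs by arm, inflates the placebo count and so hides an excess on liraglutide. The documents do not support this. The figures of about 31% (placebo) and 25% (liraglutide) in SAP 2.1 are treatment discontinuations observed in trial NN8022-1839. For this trial the plan uses a single figure: "The calculated sample size ensures adequate power if the proportion of discontinuing subjects should be as high as 30"%. Stopping drug is not leaving the trial, and subjects who withdraw consent are to be offered procedures like those of the end-of-treatment visit (Protocol 8.1). How many subjects in either arm would have only one value is unknown.

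Nor can spurious persistent cases be counted. That would need a rate of chance crossings, which the documents do not give. An assumed 2% to 10% per sample would be too high for the four of five criteria set at 20 or 50 ng/L. In the thyroid-nodule cohort cited in Appendix A, 20–50 ng/L occurred in up to 1%, 50 to below 100 in 0.14%, and 100 or more in 0.15%. That is at most 1 + 0.14 + 0.15 = 1.29% at 20 ng/L or above, and 0.14 + 0.15 = 0.29% at 50 ng/L or above. Independence between visits is also doubtful, because several confounders that Appendix A lists, such as smoking and renal dysfunction, tend to be stable within a person.

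**Conclusion.** The definition does not measure persistence in two situations: a rise that starts after the first post-baseline sample and continues, and a subject whose only post-baseline value is raised. A subject with one raised value among several is not affected; that subject is correctly incidental only. Both results follow from the wording. The first assumes at least two planned post-baseline samples, which the documents imply but the available text does not number.

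The consequence is modest. What is lost is the ability to tell lasting from passing rises below 20 ng/L in a descriptive safety table. No test, endpoint or subject-level action depends on it, and no size in subjects can be given. It is a cheap improvement, not a flaw that threatens the trial's safety conclusions.

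**What to change.** In SAP 2.4.3.2, under Calcitonin:

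1. Add a row, for each of the five criteria, for subjects raised at two or more consecutive post-baseline measurements and at every measurement from the first raised value to the last available.
2. Report subjects with only one post-baseline calcitonin value separately, by arm, with the number raised.
3. State whether samples taken after stopping trial product count towards the classification.
4. Keep the present every-value and at-least-one rows, so that the table stays comparable with others built on the same definition.

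A rise first seen at the last sample stays unconfirmed under the new row and remains in the at-least-one row. The benefit for late rises needs at least three planned samples, so check K against the flow chart.

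The cost is SAP wording, one derived flag and one extra row per criterion, all from data already collected. No visit, endpoint or significance level changes.
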